**To determine the impact of mindfulness on post-stroke cognitive impairment:**

- The MoCA and cognitive battery will be administered at 1 and 6 months post-stroke. T-tests and chi square analysis will compare cognitive performance (MoCA, global cognitive score, and individual cognitive tests) pre- and post-intervention for each group (MoCA cutoff <26), and MBSR v SSG participants at each time point.

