**To determine the effect of MBSR on abnormal cerebral activation patterns on MEG after stroke:**

- Participants will undergo neuroimaging at 1 and 6 months post-stroke. Participants in the MBSR and SSG will be compared to a previously collected group of controls with no infarct. Source localized whole brain activation will be assessed to determine overall differences in space and time between each group (MBSR v SSG) versus controls for each time point. Cluster-based permutation tests (based on independent measures t values) will then be performed to evaluate mean differences in activation for ROIs between groups at each time point. Paired t values will allow for evaluation of changes over time within each group. Amplitude of peak activation and spike latency will be assessed. ANCOVA will allow for adjustment of potential confounders.
- *Sample Size.* We have been able to demonstrate results at or approaching statistical significance for our current cohort of patients with minor stroke versus controls after enrolling only 9 participants. This number is similar to many other published studies evaluating differences in activation patterns on MEG. We do anticipate less of a difference when comparing stroke patients to other stroke patients, and will therefore increase our sample size to at least 20 individuals in each group. There remains a chance given the potential for improvement in both groups, that we may still be inadequately powered to detect long-term outcomes in this pilot study; however results will also allow treatment effect estimates that will inform a larger clinical trial.

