**To determine the impact of mindfulness on post-stroke depression:**

- Participants will be administered the PHQ-9 pre- and post-intervention. Paired t-tests will be used to evaluate for significant differences in scores between time points using each score as a continuous variable. Chi square analysis will be used to evaluate presence or absence of moderate depression (PHQ9 score >9). Independent t-tests and chi square analysis will compare scores of MBSR versus SSG participants for each time point.
- *Sample Size.* Based on prior MBSR studies, we anticipate that this will show a greater clinical effect than change in MoCA, giving us more than adequate power to detect differences with this sample size.

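### No paired test is named for before-and-after MoCA <26 status (or, apparently, PHQ-9 >9 status); an ordinary chi-square would be conservative and can miss within-arm change

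*Combined protocol and SAP*

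**What the plan says.** Two paragraphs of Section 7 (Study Statistics) matter.

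**Cognition.** "The MoCA and cognitive battery will be administered at 1 and 6 months post-stroke", so each patient contributes two measurements. The next sentence reads "T-tests and chi square analysis will compare cognitive performance (MoCA, global cognitive score, and individual cognitive tests) pre- and post-intervention for each group". Its ending assigns the same pair of methods to two different comparisons: "pre- and post-intervention for each group (MoCA cutoff <26), and MBSR v SSG participants at each time point". It does not say whether the t-tests are paired, or what form the chi-square takes for the comparison over time.

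**Depression.** Three sentences follow one another.
- For the score over time: "Paired t-tests will be used to evaluate for significant differences in scores between time points using each score as a continuous variable".
- For the cut-off: "Chi square analysis will be used to evaluate presence or absence of moderate depression (PHQ9 score >9", with no comparison stated.
- For the arms: "Independent t-tests and chi square analysis will compare scores of MBSR versus SSG participants for each time point".

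The planned size is to "increase our sample size to at least 20 individuals in each group". No significance level, expected proportion below or above either cut-off, correlation or numerical power is given. Neither McNemar's test nor any other paired binary method is named anywhere.

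**The concern.** Within an arm, before-and-after status is paired: each patient is above or below the cut-off at one month and again at six. The ordinary chi-square treats the two sets of classifications as coming from different people. If status is positively correlated over time, as repeated measures on one person usually are, the test overstates the variance of the change and rejects too rarely.

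The plan says that a test is paired when it means so, for the PHQ-9 score and for within-group MEG change. The cognition sentence lacks the word, and an analyst following it could reasonably run the ordinary test.

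MoCA performance and depression are listed among the primary clinical outcomes. The pandemic section makes cognition the only outcome measure for participants whose MEG cannot go ahead. With about 20 patients per arm there is little information to spare. Between the arms, the cut-off test also stands beside the t-test with no statement of which one leads.

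**Working it through.** **Inputs.** From the documents: at least 20 patients per group, so 20 pairs per within-arm test; cut-offs of MoCA <26 and PHQ-9 >9. Assumed, because the documents give none: two-sided 5% level; proportion below or above the cut-off 20–60%; phi, the correlation between a patient's two binary statuses, 0 to 0.7. The plan states no error rate or power for these tests, so there is no figure to reproduce.

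**Large-sample size.** With a true proportion p at both visits, the variance of the difference is 2p(1−p)(1−phi)/n. The ordinary chi-square uses 2p(1−p)/n. Its actual size is therefore 2 × [1 − Φ(1.96/√(1−phi))].
- phi 0.1: 1.96/0.949 = 2.07, size 3.9%
- phi 0.3: 1.96/0.837 = 2.34, size 1.9%
- phi 0.5: 1.96/0.707 = 2.77, size 0.56%
- phi 0.7: 1.96/0.548 = 3.58, size 0.035%

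**Exact size at n = 20.** Let a be the probability of being impaired at both visits: a = p1·p2 + phi·√[p1(1−p1)p2(1−p2)]. The two discordant probabilities are p1 − a and p2 − a. Every possible paired table was enumerated and weighted by its multinomial probability. Ranges are over p = 20–60% (60% mirrors 40%).

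| phi | ordinary chi-square | mid-p McNemar | exact McNemar |
|---|---|---|---|
| 0.1 | 3.3–4.2% | 3.1–4.1% | 1.2–2.1% |
| 0.3 | 1.7–2.1% | 2.1–3.6% | 0.7–1.7% |
| 0.5 | 0.5–0.8% | 1.0–2.6% | 0.2–0.9% |
| 0.7 | 0.06–0.13% | 0.2–0.9% | 0.03–0.2% |

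At phi 0 the ordinary chi-square has size 4.3–5.3%, so nothing is lost there.

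**Power at n = 20**, by the same enumeration. Example: 60% to 30% at phi 0.5 gives a = 0.18 + 0.5 × 0.2245 = 0.292, and discordant probabilities 0.308 and 0.008. Each cell shows ordinary chi-square / exact McNemar / mid-p McNemar, in %.

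| change | phi 0.1 | phi 0.3 | phi 0.5 |
|---|---|---|---|
| 60% to 30% | 46 / 37 / 47 | 46 / 45 / 58 | 44 / 56 / 73 |
| 40% to 20% | 28 / 17 / 26 | 25 / 19 / 30 | 21 / 20 / 35 |
| 30% to 10% | 35 / 19 / 31 | 33 / 20 / 34 | 29 / 20 / 37 |

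At phi 0.5 mid-p McNemar gains 8 to 29 percentage points. At phi 0.3 the gain is 1 to 12 points. At phi 0.1 it is between +1 and −4. Exact McNemar is often no better than the ordinary chi-square, and sometimes worse.

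**More patients do not cure it.** At n = 40 and phi 0.5 the ordinary chi-square still has size 0.6–0.7%. For 40% to 20% its power is 49%, against 79% for mid-p McNemar.

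**The case against.** The strongest reply is that the plan never calls the test unpaired. McNemar's test is itself a chi-square test, and the authors use pairing elsewhere, so the wording may only be incomplete. That stands: a reader might infer that the plan specifies an invalid test, but the text shows only that the form is left open. For PHQ-9 the case is weaker still. The cut-off sentence names no comparison. Its place after the paired t-tests, and before a separate sentence on the arms, suggests before-and-after use without stating it.

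A second reply is that the loss depends on an assumed correlation. That also stands. A blanket claim of an error rate under 1%, or of a general loss of power, is not supported: both need moderate or high correlation, and the power loss is against mid-p rather than exact McNemar.

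A third reply is that little hangs on it. The error is conservative, within-arm change does not estimate the MBSR effect, and the PHQ-9 score over time already has a paired test. The study calls itself a pilot and concedes that power may be inadequate. All this limits the weight of the point. It does not justify leaving the test unnamed.

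A reader might also infer that the randomised comparison is invalid. It is not. The arms are independent, so a chi-square between them is sound, only less efficient than the score. At an assumed standardised difference of 0.8 with 20 per arm, power is 69% for the t-test and about 49% after a split near the median.

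**Conclusion.** The point holds as a gap in specification with a quantifiable consequence. The cognition paragraph assigns a chi-square to paired binary data without naming a paired form; the depression paragraph probably does the same. If the ordinary test is run with 20 patients, its size falls from a nominal 5% to about 3–4% at phi 0.1, 2% at phi 0.3, 0.5–0.8% at phi 0.5 and 0.1% at phi 0.7. At phi 0.5 power drops from 73% to 44% (60% to 30%), from 35% to 21% (40% to 20%) and from 37% to 29% (30% to 10%), relative to mid-p McNemar. At phi 0.1–0.3 there is little or no difference for some rates.

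The level, rates and correlations are assumptions. The consequence is confined to missed within-arm change: there is no excess of false positives, and the MBSR versus SSG tests are not invalidated. It is worth correcting because the correction is nearly free.

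**What to change.** In Section 7:

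1. In the cognition and depression paragraphs, name the mid-p McNemar test for before-and-after MoCA <26 and PHQ-9 >9 status within each arm, and state the significance level. Exact McNemar is not a good substitute, being about as conservative as the ordinary chi-square at this size.
2. In the cognition paragraph, say that before-and-after scores are compared with paired t-tests, as the depression paragraph already does.
3. In the depression paragraph, say which comparison the cut-off sentence refers to.
4. For MBSR versus SSG, make the post-intervention MoCA and PHQ-9 scores, adjusted for their baseline values by ANCOVA, the main analysis. Baseline scores are already collected, and ANCOVA is already planned for MEG. Keep the cut-off proportions as supportive, with a risk difference and confidence interval.

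The cost is wording and slight extra analysis, with no new data. One drawback is that mid-p McNemar does not strictly guarantee the nominal level. At n = 20 its computed size was at most 4.1% for phi 0.1 to 0.7 (4.2% at phi 0), and at n = 40 at most 4.7%.

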## 2. Objectives

Objective 1: To determine the effect of MBSR on abnormal cerebral activation patterns on MEG after stroke. Participants will undergo neuroimaging pre- and post-intervention. We will evaluate differences in activation patterns both at rest and during a visual cognitive task using cluster-based permutation tests. Patients in the MBSR and SSG groups will be compared to one another and to patients with no infarct

(previously collected cohort). T-tests and ANCOVA will be used to determine differences between groups at each time point. Functional connectivity studies will also be performed to evaluate differences between groups.

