**Objective 2: To determine the impact of mindfulness training on post-stroke cognitive impairment.**

Participants will be administered a pre- and post-intervention Montreal Cognitive Assessment (MoCA), along with a battery of cognitive tasks to measure attention, concentration, processing speed, and executive function. Performance will be compared pre- and post-intervention, and for MBSR versus SSG participants.

**Objective 3: To determine the impact of mindfulness training on post-stroke depression.** The PHQ9 will be given to patients pre- and post-intervention and compared across groups at each time point.

*As secondary objectives we will also evaluate patient satisfaction scores, measures of functional recovery: the modified Rankin scale (mRS) and Barthel Index (BI), and the likelihood of successful return to work.*

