## 7. Study Statistics

- a. Primary outcome variables include: MEG- changes in spectral properties and an estimate of the localization of spontaneous brain activity during resting state, functional connectivity during resting state. Clinical- performance on the MOCA and other cognitive measures (as part of the Recovery Study), patient-reported outcomes: fatigue, depression, satisfaction, quality of life.
- b. Secondary outcome variables include: changes in spectral properties, spontaneous brain activity, and functional connectivity during completion of various cognitive tasks.
- c. We will use an intention-to-treat analysis; however, we will adjust for degree of participation and consider an additional exploratory per-protocol analysis. For those lost-to-follow-up, data will be censored at the time they are lost. In addition to the proposed analyses, if there is evidence for an uneven distribution of confounding factors across treatment and control groups, we will perform multivariable linear regression to adjust for confounders (eg. degree of participation, age, sex, level of education, antidepressant use, and major medical co-morbidities (Charlson Comorbidity Index)).

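### MoCA, cognitive and PHQ-9 scores are compared between arms without adjusting for the baseline score that the trial already collects

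*Combined protocol and SAP*

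**What the plan says.** For cognition (Section 7, cognitive impairment), the MoCA, a global cognitive score and the individual tests are measured at 1 and 6 months. They are compared by t-test and chi square "pre- and post-intervention for each group (MoCA cutoff <26), and MBSR v SSG participants at each time point". So there are pre/post tests inside each arm, and separate between-arm tests at each visit.

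For depression (Section 7, depression), the between-arm analysis is: "Independent t-tests and chi square analysis will compare scores of MBSR versus SSG participants for each time point". The pre/post analysis is: "Paired t-tests will be used to evaluate for significant differences in scores between time points using each score as a continuous variable". The text does not say whether those paired tests are run by arm or on all participants together. Objective 3 in Section 2 has the same structure: "The PHQ9 will be given to patients pre- and post-intervention and compared across groups at each time point".

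Four other provisions might have supplied an adjusted analysis:

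- Section 7c says "we will adjust for degree of participation and consider an additional exploratory per-protocol analysis".
- Section 7c also adds a multivariable linear regression, but only "if there is evidence for an uneven distribution of confounding factors across treatment and control groups". Its examples of covariates are participation, age, sex, education, antidepressant use and comorbidity.
- ANCOVA appears under Objective 1 ("T-tests and ANCOVA will be used to determine differences between groups at each time point") and in the MEG part of Section 7 ("ANCOVA will allow for adjustment of potential confounders"), both for MEG.
- The regressions at the end of Section 7 concern perception of recovery, satisfaction and quality of life, with mRS and BI as covariates.

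**The concern.** The hypothesis in the Abstract is between arms: better scores after MBSR than after the support group. The plan estimates this only by comparing follow-up means. The baseline score, usually the most obvious predictor of the follow-up score, is collected and then left out of that comparison.

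The pre/post tests do not fill the gap. A change within one arm, or in both arms pooled, is not an estimate of the difference between arms, and Section 7 itself expects that both groups may improve. Nothing in the plan marks these tests as descriptive, so a significant change in one arm and not in the other could be read as a treatment effect.

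Section 7a lists the MoCA, the other cognitive measures and depression among the primary clinical outcomes. The pandemic section lets cognitive outcomes stand alone for participants whose MEG is suspended. Section 7 also calls the study a pilot that may be underpowered and whose effect estimates will inform a larger trial. The precision of those estimates is therefore a main product of the study.

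**Working it through.** **Coverage in the text.** None of the four provisions supplies the adjustment. Degree of participation is a post-randomisation variable and cannot stand in for baseline. The conditional regression has an open list of covariates, so the baseline score could be added, but only after the data had been seen. ANCOVA is tied to MEG. The final regressions address other outcomes.

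**Inputs.** From the documents: at least 20 per group (Section 7, MEG sample size). That number cannot be reproduced, because no alpha, power, SD, effect size or pre/post correlation is given. Assumed here: two-sided 0.05, 80% power, outcome SD 1, normal scores, no dropout, and a baseline to follow-up correlation r of 0.3 to 0.7.

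**Formulas**, with n = 20 per arm:

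- Follow-up t-test: variance of the difference 2/n = 0.100, SE 0.316, 38 df.
- ANCOVA: variance (2/n)(1 − r²)f, 37 df. The factor f = 1 + χ²(1)/χ²(38) is the cost of estimating the slope. Its mean is 1 + 1/(2n − 4) = 1 + 1/36 = 1.028, and its square root averages 1.014. Power is averaged over f.
- t-test of change: variance (2/n) × 2(1 − r), 38 df.

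Power comes from the noncentral t distribution.

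| | t-test | ANCOVA r = 0.3 | 0.5 | 0.6 | 0.7 |
|---|---|---|---|---|---|
| Detectable difference, 80% power (SD) | 0.909 | 0.880 | 0.799 | 0.738 | 0.659 |
| Power for 0.5 SD | 34% | 36% | 42% | 48% | 57% |
| 95% CI half-width (SD) | 0.64 | 0.62 | 0.56 | 0.52 | 0.46 |
| t-test n per arm giving the same detectable difference | 20 | 21.3 | 25.6 | 29.8 | 37.2 |

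The last row means that adjustment is worth about 6%, 28%, 49% and 86% more patients (for example 25.6/20 = 1.28).

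Example, CI half-width at r = 0.5: 2.026 × 0.316 × √(1 − 0.25) × 1.014 = 0.56. For the t-test: 2.024 × 0.316 = 0.64.

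**Change score as an alternative.** A between-arm t-test of change detects 1.076, 0.909, 0.813 and 0.704 SD at r = 0.3, 0.5, 0.6 and 0.7. It is worse than the planned test when r is below 0.5, and worse than ANCOVA at all four values.

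**With losses.** At an assumed 15% loss (20 × 0.85 = 17 per arm), the detectable difference is 0.991 SD by t-test and 0.962, 0.874, 0.807 and 0.720 SD by ANCOVA.

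**Chance imbalance.** The baseline difference has SD √(2/20) = 0.316, so it exceeds 0.5 SD in either direction with probability 2(1 − Φ(0.5/0.316)) = 0.114. A 0.5 SD imbalance moves the unadjusted estimate by r × 0.5, which is 0.15 SD at r = 0.3 and 0.35 SD at r = 0.7. Given that imbalance at r = 0.7, the test statistic is centred at 0.35/0.316 = 1.11 with SD √(1 − 0.49) = 0.71. The conditional type I error is then about 12% (normal approximation). Over all trials it remains 5%.

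**Break-even.** ANCOVA power for 0.5 SD is 33.0% at r = 0 and 33.8% at r = 0.17. The t-test has 33.8%.

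**The case against.** The strongest reply is that this is a matter of efficiency and not an error. Randomisation makes the follow-up contrast unbiased, its type I error over all trials is 5%, and the between-arm hypothesis is tested. That is correct, and the point should not be presented as a validity defect.

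The gain also depends on a correlation the documents do not give. The visits are months apart, entry is restricted to mRS 0-2 and NIHSS below 8, and each cognitive test may have its own correlation. At r = 0.3 the improvement is slight, and even at r = 0.7 power for 0.5 SD stays below 60%. This stands: adjustment does not make the pilot adequately powered for an effect of that size.

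Section 7c could pick up a visible baseline difference, because its covariate list is open and the planned baseline comparisons would reveal one. This softens the imbalance argument but does not remove it. The adjustment is conditional on the data, the baseline score is not named, and the routine gain in precision is not obtained.

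Finally, the MoCA and PHQ-9 are bounded, so the normal-theory figures are approximate. This applies to the planned t-tests as well. Handling of missing follow-up scores is a separate matter, which ANCOVA does not settle.

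**Conclusion.** The concern holds. For the continuous MoCA, cognitive and PHQ-9 scores, the plan specifies no baseline-adjusted treatment contrast, and no other part of the document supplies one. The consequence is lost precision and exposure to chance imbalance. At the assumed correlations of 0.3 to 0.7, the detectable difference is larger than it need be by 0.03 to 0.25 SD (0.909 minus 0.880, and 0.909 minus 0.659). The size of the loss rests on those correlations, 20 per arm, two-sided 0.05 and no dropout. The case for adjusting does not depend on where in that range the correlation lies, because the gain is positive above about 0.17 and the cost below it is negligible. This should be changed, but the planned test is not invalid.

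**What to change.** In the cognitive and depression parts of Section 7, define the treatment effect for each continuous score (MoCA, global and individual cognitive scores, PHQ-9) as the MBSR-minus-SSG difference in the post-intervention score. Estimate it by ANCOVA and report it with a 95% CI. Always include the baseline value of the same score, whether or not imbalance is seen. Do not substitute a t-test of change.

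Label the pre/post tests and the baseline between-arm comparison as descriptive, and state whether the PHQ-9 paired tests are run by arm.

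The cost is SAP wording, with no new data. The extra parameter adds about 1.4% to the standard error on average (2.8% to the variance). If the correlation were zero, power for 0.5 SD would fall only from 33.8% to 33.0%.

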**To determine the impact of mindfulness on post-stroke depression:**

- Participants will be administered the PHQ-9 pre- and post-intervention. Paired t-tests will be used to evaluate for significant differences in scores between time points using each score as a continuous variable. Chi square analysis will be used to evaluate presence or absence of moderate depression (PHQ9 score >9). Independent t-tests and chi square analysis will compare scores of MBSR versus SSG participants for each time point.
- *Sample Size.* Based on prior MBSR studies, we anticipate that this will show a greater clinical effect than change in MoCA, giving us more than adequate power to detect differences with this sample size.

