## 1. Abstract

Thrombectomy has significantly improved stroke outcomes. Nearly 80% of our clinic population now present with small strokes and low NIH Stroke Scale (NIHSS) scores. However, despite “good recoveries”, greater than 40% endorse significant problems with higher-level cognitive functions, mood disorders, and fatigue. The natural history and pathophysiology of these deficits are not as well described as motor or language deficits; but they are equally debilitating, preventing previously high-functioning active individuals from returning to their prior workplace and social environments. This can be particularly difficult for the elderly, resulting in early retirement and loss of independence. The pathophysiology underlying these deficits remains unclear. Impairments in executive function and processing speed occur independent of stroke size, location, or depression. Using magnetoencephalography (MEG), a tool able to evaluate neurophysiologic processes in real time akin to EEG with better spatial resolution, *we have found that cerebral activation patterns are slowed and more diffuse during task completion in stroke patients compared to controls*; and at rest there is **abnormal activity in the frontal lobes**, an area critical for executive function, processing speed, affect regulation, and decision making. Some patients improve over months; however, recovery is variable and by this time many have made critical life decisions. There is little data regarding effective treatment options. The ability to hasten improvement would significantly improve morbidity in a group with excellent recovery potential.

Mindfulness has been practiced since ancient times, but only recently gained popularity as an effective treatment for anxiety and depression both in normal individuals and those with chronic disease states. Mindfulness Based Stress Reduction (MBSR) has also been evaluated in a small series of patients with chronic stroke and traumatic brain injury and has *shown to improve performance during tasks of executive function*. A combination of meditation, body awareness, and yoga, MBSR is an active process thought to engage the frontal lobes. Based on our current understanding of pathophysiology, MBSR may serve as an attractive non-pharmacologic intervention to improve *subacute* post-stroke mood and cognitive dysfunction.

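### Section 7 sets pre/post tests beside MBSR v SSG tests without saying which decides Objectives 1-3, and specifies no between-arm test of change or baseline-adjusted comparison

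*Combined protocol and SAP*

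**What the plan says.** Each of the first three analysis blocks in section 7 is headed as a test of MBSR or mindfulness, for example "To determine the impact of mindfulness on post-stroke depression". Each lists two kinds of test.

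- **Pre/post tests.** For MEG, "Paired t values will allow for evaluation of changes over time within each group". For cognition, t-tests and chi-square tests will "compare cognitive performance (MoCA, global cognitive score, and individual cognitive tests) pre- and post-intervention for each group". For PHQ-9, "Paired t-tests will be used to evaluate for significant differences in scores between time points using each score as a continuous variable"; that sentence does not say whether the test is run by arm or on both arms pooled.
- **Between-group tests.** For MEG, cluster-based permutation tests will "evaluate mean differences in activation for ROIs between groups at each time point"; Objective 1 in section 2 makes clear that the two arms are compared with each other as well as with the non-stroke cohort. For cognition, tests are run "pre- and post-intervention for each group (MoCA cutoff <26), and MBSR v SSG participants at each time point". For PHQ-9, "Independent t-tests and chi square analysis will compare scores of MBSR versus SSG participants for each time point".

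Nothing in section 7 ranks these tests or calls any of them descriptive.

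On recovery without MBSR, the Abstract says "Some patients improve over months; however, recovery is variable". Section 3 says much the same, and the MEG sample-size text in section 7 allows that both groups may improve. The hypotheses in the Abstract are between-arm for all three objectives; the MEG hypothesis is that an initially abnormal pattern improves after MBSR relative to SSG.

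**The concern.** The first assessment is at about 1 month after stroke and the second at about 4-6 months. That window lies within the period when the protocol says some patients get better anyway. A pre/post difference in the MBSR arm therefore contains any MBSR effect plus whatever recovery the SSG arm also experiences, and the paired test cannot divide the two. If the PHQ-9 test is pooled over arms, it says nothing about mindfulness at all.

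The hypothesis and the tests also do not line up. The MEG hypothesis concerns improvement relative to SSG, and section 7a names changes in spectral properties among the primary MEG outcomes. Yet change over time is tested only within groups, and the between-group tests are cross-sectional.

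At stake is how mixed results would be read. The sample-size text concedes that power may be inadequate. A significant change in the MBSR arm beside a non-significant MBSR v SSG test is thus a plausible outcome, and the plan does not say which result governs. The same text says the results will supply effect estimates for a larger trial; a within-arm change used in that way would include common recovery.

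**Working it through.** **1. The plan's own figure.** Section 7 gives at least 20 per group, with no alpha, power, effect size or SD. There is nothing to reproduce.

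**2. Is change compared between arms, or baseline adjusted for, anywhere?**

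| Place | What is planned | Between-arm change or baseline adjustment? |
|---|---|---|
| Section 2, Objective 1 | t-tests and ANCOVA, group differences at each time point | No baseline covariate named |
| Section 7, MEG | Permutation tests between groups at each time point; paired values within group; ANCOVA for confounders | Change within group only; no baseline covariate named |
| Section 7, cognition | Pre/post for each group; MBSR v SSG at each time point | No |
| Section 7, depression | Paired t-tests; MBSR v SSG at each time point | No |
| Section 7c | Multivariable regression if confounders are unevenly distributed | Conditional; baseline score not among the examples |

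**3. How often would a within-arm test be significant with no MBSR effect?** Inputs: n = 20 per arm (section 7); two-sided 5% (assumed); true MBSR effect zero (assumed); the same mean change in both arms, expressed as d = mean change / SD of change (assumed, since the documents give no size).

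The paired t statistic has 19 df and non-centrality d × √20. The critical value is 2.093. The probability of significance is p = 1 − F(2.093) + F(−2.093), with F the non-central t distribution function. The arms are independent, so the probability that MBSR is significant and SSG is not is p(1 − p).

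| d | d × √20 | p | p(1 − p) |
|---|---|---|---|
| 0 | 0 | 5% | 4.8% |
| 0.3 | 1.342 | 24.7% | 18.6% |
| 0.5 | 2.236 | 56.4 to 56.5% | 24.6% |
| 0.8 | 3.578 | 92.4% | 7.0% |

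Check at d = 0.3: 0.247 × 0.753 = 0.186.

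**4. The randomised comparison in the same setting.** A simulation used 50,000 trials, 20 per arm, an assumed pre-post correlation of 0.6, and common changes of 0, 0.25, 0.5 and 0.75 SD of the score. The between-arm t-test, on post-intervention values or on change, was significant in 4.8% to 5.1% of trials. A change common to both arms cancels.

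**5. Between-arm power for context.** At 20 per arm and two-sided 5%, a two-sample t-test has 34% power for a difference of 0.5 SD and 69% for 0.8 SD; 80% power needs about 0.91 SD.

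**The case against.** The strongest reply is that the safeguard is already planned. The trial is randomised against an active comparator, MBSR v SSG tests are listed for all three objectives, and the Abstract's hypotheses are between-arm. Under randomisation, the post-intervention comparison is unbiased without any change score; baseline adjustment mainly adds precision. No passage says that a within-arm result, or MBSR significant with SSG not, would support an objective.

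All of this stands. A reader might infer that the trial will judge mindfulness by within-arm tests alone, or that its planned between-arm tests are biased. The documents support neither reading.

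What remains is narrower. Between-arm hypotheses in the Abstract do not make the between-arm test decisive in section 7, where pre/post tests appear under the effect headings with no label to distinguish them. The planned ANCOVA would meet part of the point if it named the baseline value as a covariate, but it does not, and it is listed for MEG only.

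It is also fair to say that this is described as a pilot, and that a univariate paired t-test does not represent the MEG cluster analysis. The percentages apply most directly to MoCA, the cognitive scores and PHQ-9.

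**Conclusion.** The point holds as a gap in specification. Section 7 should say which comparison decides Objectives 1-3, and it lacks a baseline-adjusted or change-based comparison between arms. The pre/post tests cannot isolate MBSR from recovery common to both arms.

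The size depends wholly on assumed inputs. For a common change of 0.3 to 0.8 SD of the change score, the MBSR-arm test is significant in 25% to 92% of trials with no MBSR effect, and MBSR alone is significant in 7% to 25%. These are rates of within-arm significance; they become rates of false conclusion only if the between-arm result is set aside.

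Three further inferences go beyond the documents:

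- **Recovery as the rule.** The text says that some patients improve, variably, and that both arms may improve. It gives no rate or size.
- **Retest gains.** Practice effects are plausible when the same tests are given twice, but the documents do not mention them.
- **Unequal task exposure against the non-stroke cohort.** This would need those controls to have been scanned only once, which is not stated. It would bear mainly on task MEG, which section 7b makes secondary.

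**What to change.** In section 7:

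1. State that Objectives 1-3 are judged on the randomised MBSR v SSG comparison of post-intervention values, adjusted for the baseline value of the same measure.
2. For MoCA, the cognitive scores and PHQ-9, specify ANCOVA with the baseline score as covariate, whether or not the arms look balanced.
3. For MEG, specify a between-arm cluster-based permutation test of baseline-adjusted post-intervention maps or of post-minus-pre maps.
4. Label the within-arm tests descriptive, and say whether the PHQ-9 paired test is by arm or pooled.
5. Label the post-intervention patient v non-stroke-control comparisons descriptive. The controls may still be shown at both time points.

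The cost is a change of wording and one extra analysis on data already collected, with no added visits or participants. The downside is that a significant within-arm change can no longer be claimed as evidence of effect.
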